6.3.11. Triheptanoin Administration

Triheptanoin administration will be accomplished in the Epilepsy Monitoring Unit located in the Children's Medical Center. Initiation will be completed under the supervision of [name] or one of the physician investigators.

6.3.12. Adherence Assessments

All C7 administration will be done on an inpatient basis, over one day. No adherence assessments are completed.

7. MANAGEMENT OF ADVERSE EXPERIENCES

Previous experience with C7 oil in different populations has yielded no serious adverse effects. Due to the limited nature of the use of C7 oil, there is no data available on how frequent the following side effects occur, nor if there are differences between normal diet or ketogenic diet.

Breakthrough Seizures: There is the possibility that the administration of C7 oil may result in the subject dropping out of ketosis very quickly, which may lead to breakthrough seizures. Management of these breakthrough seizures will follow standard of care protocol, which could include IV or rectally administered anti-convulsant medications.

Diarrhea: Subjects who experience diarrhea may be instructed to increase the amount of fiber consumed with each meal. In addition, C7 will be administered in a fat free, sugar free food item, such as yogurt or pudding, and subjects are instructed to consume this food over 30 minutes in order to minimize diarrhea. Subjects who cannot tolerate the maximum tolerable dose will be discontinued from the study.

Stomach pain: Subjects who experience stomach pain at any time during the treatment will, under the direct supervision of [name] or M.D. co-investigator, be assessed for severity. If subjects cannot tolerate the recommended dose due to severe stomach pain, they will be discontinued from the study.

Weight gain: Although weight gain is a possible side effect of C7 ingestion, it is a long-term effect, and we do not anticipate significant weight gain over the course of one day.

8. CRITERIA FOR INTERVENTION DISCONTINUATION

Triheptanoin supplementation will be discontinued if any of the following occur:

- Any of the cited or other adverse experiences become intolerable to the subject
- Metabolic syndrome develops as assessed by glucose and lipid profiles
- Any elevation above laboratory normal range in hepatic transaminases or creatinine is noted
- Any blood cell count abnormality outside laboratory normal range develops
- Non-compliance occurs

- Severe intercurrent illnesses take place
- Severe seizures that are unusual for the subject take place

Subjects who discontinue due to the above reasons will be asked to return for a final research visit to complete exit procedures and receive referrals for ongoing care if necessary. Subjects who are discontinued due to adverse events will be followed via daily, alternate-day or weekly phone calls to assess resolution of the adverse event.

9. STATISTICAL CONSIDERATIONS

9.1. General Design Issues

The main aim of this proof of principle trial is to evaluate the compatibility of C7 with ketogenic diet in subjects diagnosed with G1D. This protocol will yield data that allow a go/no-go decision regarding whether C7 should proceed to an efficacy trial:

If EEG, clinical seizure activity, glycemia and ketosis (blood beta-hydroxybutyrate level) under the ketogenic diet remain unaltered (i.e., unchanged from normal laboratory value ranges) in at least 3 out of 5 G1D subjects in each age group after the partial substitution of ketogenic diet fat with C7, we will confirm compatibility of C7 with ketogenic diet and recommend proceeding to an efficacy trial for C7.

The sample size estimation for this optimal two-stage design is given in Section 9.3.

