11.2 Subject Confidentiality	27
11.3 Study Modification/Discontinuation	27
12. ETHICAL CONSIDERATIONS.....	28
12.1 Risk/Benefit Assessment.....	28
12.2 Pediatric Populations.....	28
13. PUBLICATION OF RESEARCH FINDINGS	28
14. REFERENCES	29

SYNOPSIS

Study Title

Compatibility of triheptanoin (C7) with the Ketogenic Diet in Patients Diagnosed with Glucose Transporter Type 1 Deficiency (G1D)

Objectives

Primary Objectives: To explore triheptanoin (C7 oil; C7) compatibility with the ketogenic diet by evaluating EEG (for the determination of outcome EEG as defined below), and seizure rate, glycemia and ketosis in proven G1D patients receiving (both prior to enrolment and for the duration of this study) a ketogenic diet.

Secondary Objectives: N/A

Design and Outcomes

This is a single-site, open-label proof of principle exploratory trial to investigate the compatibility of C7 oil with the ketogenic diet in subjects genetically diagnosed with G1D. The primary outcome measure is change in EEG during C7 supplementation. The secondary outcome measures are: changes in seizure rate, glycemia (blood glucose levels), and ketosis (beta-hydroxybutyrate levels).

Interventions and Duration

This is an open-label, single arm proof of principle trial of orally-administered C7 in subjects diagnosed with G1D and currently receiving (i.e., prior to enrolment) a ketogenic diet. The ketogenic diet will have been previously prescribed by the patient's treating physician independently of this study and for clinical reasons (i.e., the treatment of G1D epilepsy). **Because the ketogenic diet supplies well over 50% of calories from fat, subjects, who are already tolerating over this much fat as part of their previously-prescribed ketogenic diet, will replace 45% of their daily caloric intake with C7** for 24 hours, during a 48 hour inpatient stay. During observation, subjects will have continuous EEG to monitor for any potential C7-related changes in seizure activity before, during, and after C7 ingestion. Subjects will undergo clinical evaluation and comprehensive blood work at baseline and discharge, and continuous EEG and evaluation of glucose and beta-hydroxybutyrate levels while inpatient and receiving C7. Total time of participation is 4 days.

Sample Size and Population

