1. STUDY OBJECTIVES

1.1. The main hypotheses tested are:

- C7 metabolism will not interfere with previously-acquired ketosis in G1D, as measured by no change in EEG from pre-C7 baseline.
- C7 metabolism will not interfere with previously-acquired ketosis in G1D, as measured by no increase in observable seizure rate and no clinically relevant changes glycemia and ketosis, as measured by random glucose levels and beta-hydroxybutyrate levels.

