late hepatic neoglucogenesis and this can decrease ketosis via insulin release (113). Neoglucogenesis stemming from heptanoate was observed by us after infusion of heptanoate in G1D mice (28). However, the relative amount of heptanoate infused was far greater than that used for G1D subjects. This was expected because a large quantity of labeled substrate is necessary to achieve labeling of brain intermediary metabolites in human and mouse ^{13}C NMR experiments as developed by us (27, 32, 114, 115). Thus, no significant neoglucogenesis (i.e., an increase in glycemia >10 mg/dl) is obligatorily anticipated after C7 ingestion.

Preliminary studies. One G1D subject has received C7 at 45% while on a 3.5:1 ketogenic diet without clinical or analytical consequence. Our 14 G1D subjects on a regular diet studied in the fasting state (8) exhibited a mean blood glucose of 88.5 ± 1.9 mg/dl (mean \pm SEM), which did not significantly change 30-60 min after ingestion of the base dose (35%) of C7 (87.8 ± 2.4 mg/dl). Beta- hydroxybutyrate levels were also unchanged (0.25 ± 0.10 mM in the fasting state relative to 0.23 ± 0.1 mM in the post-C7 state; mean \pm SEM). The same conclusion was reached after 10 of these subjects were tested after 3 months on C7. Thus, C7 metabolism does not appreciably interfere with glucose metabolism and related ketosis (beta-hydroxybutyrate) under a regular diet.

Fifteen subjects with G1D (five per each of three age groups) and currently receiving a ketogenic diet will participate. After baseline measurements of common blood analytes, EEG, and blood ketone body levels, subjects will be given triheptanoin dosed by individual daily caloric intake, divided in 4 daily fractionated doses.

All subjects will take triheptanoin for 24 hours (4 doses) on an inpatient basis.

This study, if the hypothesis is correct, will enable future combined or comparative studies because, for 1/3 of G1D patients, the ketogenic diet is insufficient and may be supplemented with C7 or replaced by it depending on future work, whereas, conversely, C7 may prove insufficient as first line therapy in some patients and necessitate the addition of a ketogenic diet.

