6.3.9. Electroencephalogram

The subjects will undergo continuous EEG recording of brain wave activity for approximately 48 hours during each inpatient stay. The EEG will involve placement of an electrode cap. The subject will be fitted with a cap containing up to 32 electrodes which rest against their scalp, and which allow their brain electrical activity (EEG) to be recorded. An additional electrode will also be placed directly to the skin in the chest. All skin preparation equipment coming into contact with skin is discarded after a single use, and electrodes and caps are cleaned and disinfected immediately after use in accordance with published guidelines. The EEG recording is harmless and painless. Only the application of the electrode cap may involve mild, temporary discomfort. At the end of the session we will remove the cap and electrodes, and help clean the skin if necessary.

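### The go rule requires EEG and seizure activity to stay unaltered, so read literally a subject who improves does not count as compatible; for seizures this contradicts the no-increase wording elsewhere

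*Combined protocol and SAP*

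**What the plan says.** The decision rule is in Section 9.1. It opens "If EEG, clinical seizure activity, glycemia and ketosis (blood beta-hydroxybutyrate level) under the ketogenic diet remain unaltered", qualifies this as "unchanged from normal laboratory value ranges) in at least 3 out of 5 G1D subjects in each age group", and concludes that the investigators will confirm compatibility and "recommend proceeding to an efficacy trial for C7".

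The Synopsis names the outcome: "The primary outcome measure is change in EEG during C7 supplementation". Its primary objective refers to EEG "for the determination of outcome EEG as defined below". Sections 1.1 and 9.2.1.1 both express the EEG hypothesis as absence of change, and Section 9.5 plans an exact binomial 95% confidence interval for the proportion of subjects whose EEG is not altered.

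For seizures, Section 1.1 states the hypothesis "as measured by no increase in observable seizure rate", and the first sentence of 9.2.1.2 repeats it. The second sentence of 9.2.1.2 speaks of the absence of clinically relevant change.

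**The concern.** The scientific question has a direction. Sections 1.1 and 9.2.1.1 ask whether C7 interferes with established ketosis, and Section 7 names the danger as loss of ketosis leading to breakthrough seizures. A rule that asks for no alteration has no direction, so an improved EEG or a fall in seizures is an alteration like any other.

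The protocol itself gives a reason to care about improvement. Section 2.1 says that "for 1/3 of G1D patients, the ketogenic diet is insufficient and may be supplemented with C7". An improvement on C7 would fit that rationale, yet under the literal rule it removes the subject from the compatible count. At stake is the recommendation on an efficacy trial, which is the one decision this pilot is designed to inform.

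The qualifier in 9.1 does not settle the matter. A laboratory range can be applied to glucose and beta-hydroxybutyrate, but not to an EEG or a seizure count.

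**Working it through.** **The plan's own figure.** Sections 9.1 and 9.3 give three age groups of five: 3 × 5 = 15, which reproduces. No power, error rate or margin is stated, so there is nothing further to reproduce.

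**The wording, side by side (paraphrased).**

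| Section | EEG | Seizures |
|---|---|---|
| 1.1 | no change | no increase |
| 9.1 (go rule) | unaltered | unaltered |
| 9.2.1.1 | no change | not covered |
| 9.2.1.2, first sentence | not covered | no increase |
| 9.2.1.2, second sentence | not covered | no clinically relevant change |
| 9.5 | proportion not altered | no proportion named |

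No EEG entry has a direction. A subject with fewer seizures satisfies 1.1 and the first sentence of 9.2.1.2 but does not satisfy 9.1 as written.

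**Count under the literal rule, nobody worse.** No assumed rate is needed.
- Each group needs at least 3 of 5 unaltered, so it can contain at most 5 − 3 = 2 improvers.
- Three improvers in one group leave 2 of 5 unaltered, and the condition is missed.
- The most improvers the rule can absorb is 3 × 2 = 6, two per group. Seven or more of 15 must put at least three in some group, so the condition is always missed.
- Three to six improvers miss it or not, depending on how they fall across the age groups.

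**Effect on the reported proportion (hypothetical data: 3 improved, 12 unchanged, 0 worse).** With exact (Clopper-Pearson) 95% intervals:
- Not altered, as in 9.5: 12/15 = 80% (52% to 96%).
- Not worsened: 15/15 = 100% (78% to 100%); the lower limit is 0.025^(1/15) = 0.782.

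**Illustration only, with assumed rates.** Let *i* be the share who improve and *w* the share who worsen. Assume independent subjects, a common rate across groups, and all other components passing. Then P(go) = [P(Bin(5, p) ≥ 3)]³, with p = 1 − w − i under the literal rule and p = 1 − w if only worsening counts. For example, p = 0.7 gives 0.8369³ = 0.586.

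| Assumed *i* | Literal, *w* = 0 | Worsening only, *w* = 0 | Literal, *w* = 5% | Worsening only, *w* = 5% |
|---|---|---|---|---|
| 10% | 0.974 | 1.000 | 0.922 | 0.997 |
| 20% | 0.836 | 1.000 | 0.721 | 0.997 |
| 30% | 0.586 | 1.000 | 0.447 | 0.997 |

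**What the EEG is compared with.** Section 6.3.9 says "The subjects will undergo continuous EEG recording of brain wave activity for approximately 48 hours" and describes the recording only; neither it nor 9.2.1.1 names a measure. The Synopsis places the outcome during supplementation, while Section 3 evaluates EEG before and after C7. By Sections 6.1, 6.2.2.2 and 6.2.2.3, admission is at noon on Day 1, C7 starts on the morning of Day 2, the last dose is that evening, and the EEG ends at about noon on Day 3. Section 5.3.3 puts about 18 hours of recording after the last dose. The second night therefore follows dosing.

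**The case against.** The best reply is that the purpose is clear from context. The rule decides compatibility, and the EEG hypothesis is tied to non-interference, so a sensible reader would not fail a subject for improving. This stands as far as intent goes. A reader might infer that the sponsor meant improvement to count as failure; the documents do not say so. But if only harm was meant, the operative sentence should say it.

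A second reply is that a rule without direction is defensible. EEG serves here as a proxy for undisturbed ketosis, and any shift shows that C7 is not neutral when added to the diet. That is a coherent design choice for EEG, and tabulating improvements preserves the information. It does not explain why seizures have a direction in 1.1 and none in 9.1.

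Third, the two sentences of 9.2.1.2 might be read as contradicting each other. That is too strong: the second restates the first and can be read consistently with it. The firm contradiction is with 9.1.

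Fourth, nothing shows that improvement is likely. Section 12.1 anticipates no direct benefit, and exposure is four doses in one day. This is right, and it limits how much the illustrative probabilities can carry.

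Finally, without a named EEG measure neither better nor worse can be judged. That is a separate gap, and changing the direction alone would not make the rule usable.

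**Conclusion.** The point holds as a defect of wording in a rule that drives a decision. Followed literally, 9.1 can miss its go condition with no subject worse: three improvers in one age group suffice, and seven of 15 always do. For seizures it contradicts the hypothesis in 1.1 and the first sentence of 9.2.1.2. These results rest only on the stated 3-of-5 rule and on reading unaltered literally.

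Three stronger readings are not supported. First, missing the condition is not stated to mean no-go: 9.1 speaks of a go/no-go decision but spells out only the go branch. Second, the P(go) values are not estimates of this trial's behaviour, because the documents give no improvement or worsening rate. Third, nothing here extends to glucose or beta-hydroxybutyrate, where limits on change in either direction are not disputed.

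The exploratory label in 9.3 explains why the sample size is not justified. It does not excuse an ambiguous decision rule. The change should be made; confidence is medium, because intent probably already points the same way.

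**What to change.** - In 9.1, 9.2.1.1 and 9.5, and for consistency in 1.1 and 9.2.1.2, state the EEG and seizure components as not worsened from the subject's own pre-C7 baseline. For seizures, use the sponsor's no-increase wording throughout.
- Name the EEG measure and say which direction is worse, so that the rule can be applied and the Synopsis reference to a definition has something to point to.
- In 9.5, report the exact binomial interval for the proportion not worsened, and tabulate improvements separately.
- Reconcile the Synopsis with Section 3 on whether EEG is judged during or after C7, and do not label the night after the last dose as on-C7.
- Leave the glucose and beta-hydroxybutyrate limits unchanged.

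The cost is text in five sections and one extra table, with no new visits, procedures or recordings. Choosing and describing the EEG measure takes more work than the wording edits and must come first. The downside is that the rule no longer flags improvement as a change; the separate table covers this.

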3. STUDY DESIGN

This is an open-label, proof of principle trial of C7 in subjects with G1D and currently on ketogenic diet.

Fifteen subjects with G1D receiving ketogenic diet will be enrolled. Subjects will undergo baseline and exit clinic procedures in the Neurology Outpatient Clinic located in the Children's Medical Center Ambulatory Care Pavilion. Inpatient procedures including blood draws will be completed in the Children's Medical Center Epilepsy Monitoring Unit (EMU). These facilities can accommodate both pediatric and adult patients.

Evaluation of EEG will be accomplished at the pre- and post-C7 assessments. Evaluation of random glucose and beta-hydroxybutyrate levels will be accomplished at the baseline, 4 on-treatment, and exit assessments.

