6.2.2. On-Study/On-Intervention Evaluations

6.2.2.1. Entry Day 1

Subjects will be admitted for a 48 hour inpatient stay for oil administration and monitoring. Entry evaluations will be done within a day of pre-entry and consist of a nutritional assessment, and a blood draw to evaluate hematology and blood chemistry, including a random glucose. We will also obtain blood that is left over from the samples above (if available) or draw an additional 3 mL of blood, if needed, to measure C7 ketones. The collection of this blood for measurement of ketones is optional. A continuous EEG will be completed on subjects over the 48 hour inpatient stay. A peripheral IV will be placed to allow for immediate treatment of breakthrough seizures, should they occur.

6.2.2.2. Day 2

Subjects will be administered C7 starting on the morning of Day 2. Subjects will be given oil at a rate of 45% of their daily caloric intake, divided into 4 doses (breakfast, lunch, dinner, and before bed). A clinical assessment and a side effect assessment will be done. Subjects will be maintained on continuous EEG for the duration of C7 administration. Subjects will receive their final dose in the evening on Day 2. Subjects will have a blood draw to evaluate hematology and blood chemistry. Subjects will undergo a random glucose and beta-hydroxybutyrate level in the morning with their first dose of C7 and at bedtime with their last dose of oil. We will also obtain blood that is left over from the samples above (if available) or draw an additional 3 mL of blood, if needed, to measure C7 ketones. The collection of this blood for measurement of ketones is optional.

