6.2.2.3. Day 3 (Intervention Discontinuation Evaluations)

Subjects will remain inpatient until approximately noon on Day 3 to ensure no untoward withdrawal effects from C7. A clinical assessment, a side effect assessment, and a seizure count will be done. Subjects will have a blood draw to evaluate hematology and blood chemistry. Subjects will undergo a random glucose and beta- hydroxybutyrate level in the morning and just prior to discharge. We will also obtain blood that is left over from the samples above (if available) or draw an additional 3 mL of blood, if needed, to measure C7 ketones. The collection of this blood for measurement of ketones is optional. EEG will be stopped just prior to discharge.

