9.2.1.2. Laboratory Assessments

C7 metabolism will not interfere with previously-acquired ketosis in G1D, as measured by no increase in observable seizure rate and no clinically relevant changes glycemia and ketosis, as measured by random glucose levels and beta-hydroxybutyrate levels, which will remain within the pre-enrollment clinically acceptable ranges (i.e., the new values will typically be within 2SD of previous values, using as SD the SD of the normal values as determined by the laboratory).

Subjects will experience no clinically relevant changes in observable seizures, random plasma glucose, or beta-hydroxybutyrate levels, as compared to the baseline values defined above.

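### The go/no-go rule in 9.1 judges ketosis against normal laboratory ranges, contrary to 9.2.1.2 and the study hypothesis; if on-diet beta-hydroxybutyrate is above normal, preserved ketosis fails it

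*Combined protocol and SAP*

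**What the plan says.** **Decision rule.** Section 9.1 holds the only go/no-go rule. C7 is declared compatible with the diet, and an efficacy trial recommended, if EEG, clinical seizures, glycemia and ketosis (blood BHB) "remain unaltered (i.e., unchanged from normal laboratory value ranges) in at least 3 out of 5 G1D subjects in each age group". The parenthesis opens with *i.e.*, so it reads as the definition of *unaltered* for all four components.

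**Outcome definition.** Section 9.2.1.2 uses another reference for glucose and BHB: values "which will remain within the pre-enrollment clinically acceptable ranges", explained as typically being "within 2SD of previous values, using as SD the SD of the normal values as determined by the laboratory".

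**Hypothesis.** Section 1.1 states: "C7 metabolism will not interfere with previously-acquired ketosis in G1D, as measured by no increase in observable seizure rate", together with no clinically relevant change in glucose or BHB.

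**Analysis.** Section 9.5 reports the proportion of patients with *stable* glucose and BHB and does not define the word.

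**Samples.** Section 3 says that random glucose and "beta-hydroxybutyrate levels will be accomplished at the baseline, 4 on-treatment, and exit assessments". Section 6.2.2.2 times the Day 2 draws: "random glucose and beta-hydroxybutyrate level in the morning with their first dose of C7 and at bedtime with their last dose of oil". Two more draws follow on Day 3, in the morning and before discharge, in the section headed "Day 3 (Intervention Discontinuation Evaluations)".

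**The concern.** The trial asks whether ketosis that is already present survives a day of C7. Section 6.3.10 describes BHB as a ketone body that ketogenic diets generate, and Section 7 names falling out of ketosis as the risk. A population normal range is the wrong yardstick for that question: a subject in ketosis may be outside it before the first dose, and the rule does not then measure change.

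Ketosis is one of four conditions that must all hold for a go, so misclassifying it can settle the decision by itself. With two unreconciled definitions and no deciding sample named, the classification could also be chosen after the results are known.

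**Working it through.** **Inputs from the documents.** Three age groups of 5, total 3 × 5 = 15 (9.3). Threshold 3 of 5 in each group (9.1). Tolerance 2 laboratory SDs around previous values (9.2.1.2). The only BHB figures are for 14 subjects on a regular diet, mean ± SEM: "0.25 ± 0.10 mM in the fasting state relative to 0.23 ± 0.1 mM in the post-C7 state" (2.1).

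**Not in the documents.** On-diet BHB, and the laboratory's normal range and SD for BHB. No sample-size calculation can be reproduced, because 9.3 states that the size is not justified.

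**Assumption A.** On-diet BHB is above the laboratory's upper limit. Values of 2 to 5 mM are used for illustration, with 4 mM as the worked case.

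**Step 1: ketosis preserved.** BHB is 4 mM before and after C7.
- 9.1, literal: 4 mM is outside the normal range, so the subject is altered.
- 9.2.1.2: the change is 0, and 0 ≤ 2 × SD for any SD, so the subject is unaltered.

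The rules disagree whatever the SD.

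**Step 2: effect on the decision.** If all 15 subjects keep their ketosis, 0 of 5 pass in each group, against the 3 of 5 required, so P(go) = 0. This holds whether the four components are counted jointly per subject or one at a time. Assumption A need not hold for everyone: if 3 of 5 subjects in any one group stay above range, at most 5 − 3 = 2 can pass there and the answer is no-go.

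**Step 3: ketosis lost.** BHB falls from 4 to 0.25 mM. **Assumption B:** 0.25 mM lies inside the laboratory range. Section 2.1 gives it as a regular-diet mean, not as a laboratory limit. The result under 9.1 depends on which values are judged.

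| BHB before → after (mM) | 9.1, post-C7 value only | 9.1, in range before and after | 9.2.1.2 |
|---|---|---|---|
| 4 → 4 | altered | altered | unaltered at any SD |
| 4 → 0.25 | unaltered | altered | altered unless SD ≥ 1.875 mM |

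The break-even SD is (4 − 0.25)/2 = 1.875 mM. For starting values of 2 and 5 mM it is 0.875 and 2.375 mM. As a rough stand-in for the laboratory SD, the regular-diet data give 0.10 × √14 = 0.374 mM, so 2 SD = 0.748 mM. On that scale 9.2.1.2 would catch the loss.

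**Step 4: can 9.2.1.2 simply take over?** Not as written.
- *Typically* is not a criterion.
- The reference is a pre-enrollment range, not a sample.
- The SD of normal values may be the wrong scale at ketotic levels. A move from 3.0 to 2.5 mM (0.5 mM) is altered at an assumed SD of 0.075 or 0.125 mM (2 SD = 0.15 or 0.25 mM) and unaltered at 0.374 mM (2 SD = 0.748 mM).

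**Step 5: which samples?** A pre-C7 BHB is planned. Section 2.1 puts baseline ketone bodies before the first dose, Section 3 lists a baseline BHB, and 6.3.10 includes BHB in the chemistry profile that 6.1 schedules on Day 1. What is missing is a statement that this sample is the reference. Of the four draws that Section 3 calls on-treatment, the first coincides with the first dose and both Day 3 draws follow the last dose. No available section says which of them decide or how several values become one pass or fail.

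That choice matters. For illustration, assume each draw passes independently with probability 0.9 and all must pass. The per-subject probability is p = 0.9^k for k draws, and P(go on this component) = P(Bin(5, p) ≥ 3)³: 0.975 for k = 1, 0.856 for k = 2, 0.666 for k = 3.

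**The case against.** The best defence is that the intent is clear. A laboratory range cannot apply to EEG or seizures, which the same parenthesis covers, so strict literalism cannot have been meant. Sections 1.1 and 9.2.1.2 both point to change from the subject's own earlier values, and the 9.1 phrase may be loose shorthand for that. This is probably the right account of the intent. It does not repair the plan: 9.1 is the only go/no-go rule, it presents the normal range as its definition, and 9.2.1.2 is not precise enough to replace it.

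Two stronger readings are tempting and should not be adopted.
- *The rule rewards loss of ketosis.* A reader might infer that a subject who drops to a regular-diet level passes 9.1. That needs assumptions A and B and also that the post-C7 value alone is judged. The rule says *remain*. If values must be in range before and after, loss of ketosis fails 9.1 as well, and the only error is a false no-go. The documents do not settle which reading applies.
- *No baseline BHB is planned.* A reader might infer this because the dedicated BHB row in 6.1 has no Day 1 entry and 6.2.2.1 names only glucose. Sections 2.1, 3 and 6.3.10, read with the chemistry row in 6.1, show otherwise.

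It can also be said that this is an exploratory pilot, largely descriptive, with EEG and seizures judged separately and raw BHB still visible. That limits the harm to interpretation, but 9.1 still commits to a recommendation on this count.

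**Conclusion.** Wrong as written. The conflict between 9.1 and 9.2.1.2, and the absence of named deciding draws, stand on the text alone.

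The numerical consequence rests on assumption A. Under it, a subject with unchanged BHB fails 9.1 and passes 9.2.1.2 at any SD, and full preservation of ketosis in all 15 subjects gives 0 of 5 per group and no possible go. The hypothesis could be true and the rule would still reject it.

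A false go on lost ketosis is only conditional: it needs assumption B and a reading that judges the post-C7 value alone. It should not be presented as what the rule does.

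**What to change.** - **9.1:** delete the parenthesis that ties *unaltered* to normal laboratory ranges, and refer to one per-subject definition in 9.2.1.2. Use the same definition for *stable* in 9.5.
- **9.2.1.2, reference:** compare post-C7 glucose and BHB with the subject's own named pre-C7 value: the Day 1 blood, plus the Day 2 morning draw only if taken before the first dose. Replace the pre-enrollment wording with that sample and remove *typically*.
- **Allowed change:** have the investigators set it for each analyte before data are seen, and say whether a rise in BHB counts as altered.
- **Deciding draws:** name them (Day 2 bedtime, Day 3 morning, Day 3 discharge), say whether all must pass, and say how any extra BHB from the Day 2 or Day 3 chemistry profile is treated.
- **EEG and seizures:** judge each against its own pre-C7 baseline.
- **Subjects not in ketosis before C7:** state in advance how they enter the 3-of-5 count. Counting them as failures makes a go harder; counting them like the others credits preservation of something that was absent.

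The cost is wording in three sections and at most one BHB assay on Day 1 blood already drawn. The downside is that a rule fixed in advance removes later flexibility.
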